9.3.3 Replacement of Withdrawn Patients

Patients withdrawn before randomization will be regarded as screen failures. A sufficient number of patients will be screened until the pre-defined number of randomized patients has been reached. Randomized patients will not be replaced. However, patients prematurely withdrawn from treatment should be encouraged to continue to participate in the clinical trial until the scheduled end. The eligibility of prematurely withdrawn patients for the different analysis populations will be determined in a blind data review meeting with consideration of the definition of these analysis populations provided in [Section 14.1](#).

9.3.4 Follow-up of Withdrawn Patients

All patients withdrawn from IMP should be followed for AEs and SAEs for a further 4 weeks from the time of withdrawal. In case of patient consent withdrawal, the patient will be encouraged to complete an EoS Visit ([Section 13.2.5](#)).

10 TREATMENT OF PATIENTS

Patients will receive L-CsA (either 10 mg, 5 mg or 0 mg bid) in addition to SoC as prescribed by the treating physician and as described in [Section 8.3.2](#). L-CsA will be administered as 10 mg/2.5 mL, 5 mg/1.25 mL, or 0 mg/2.5 mL inhalation via the L-CsA **CCI** for up to 12 weeks.

Any changes in SoC treatment will be documented in the eCRF.

10.1 Concurrent Treatment or Medication

All participants will maintain their usual care throughout the course of the study. SoC includes prophylaxis against common opportunistic infections, immunosuppression, and any other chronic medication. All concurrent treatment or medications given within 30 days prior to Randomization until EoS (Visit 6) will be recorded in the eCRF, this also includes vaccination for SARS-CoV-2.

10.1.1 Prophylaxis and Therapy of Infections

All patients will receive standard infectious disease prophylaxis and therapy consisting of appropriately targeted antibiotics, antivirals and/or antifungals according to institutional standards. Dates of start and stop or change in dosage will be recorded on the respective eCRF.

10.1.2 Immunosuppression

Immunosuppressive therapy is permitted and will be performed to centers' standard regimen.

The use of different formulations of aerosolized Cyclosporine A other than L-CsA is strictly prohibited during the complete clinical trial period. Systemic administration of CsA is permissible if medically necessary at the discretion of the investigator.

10.1.3 Treatment for BOS

The following medications will be permitted:

- Inhaled corticosteroids are allowed and patients should be on a stable dose for 4 weeks prior to randomization and throughout the study.
- For all other inhaled medications please refer to [Section 10.1.4](#).
- Systemic corticosteroid treatment for BOS (or cGVHD) will be permitted, but a pulse dose has to be completed prior to screening.
- Extracorporeal photophoresis (ECP) for treatment of BOS is permitted within 4 weeks prior to randomization.
- Montelukast will be permitted, but patients should be on a stable dose for 4 weeks prior to randomization and throughout the study.

10.1.4 Other Medication

All inhaled medications, except investigational inhaled medications, are permissible during the trial.

Patients on bronchodilators should be on a stable dose 4 weeks prior to randomization and throughout the study. All other inhaled medication should be administered after spirometry in the following order: inhaled corticosteroids, inhaled antifungals/antibiotics, and then inhaled IMP. For details with regard to spirometry measurements, please refer to [Section 11.1.1](#).

10.1.5 Prohibited Medication

Azithromycin will not be permitted. In the event a patient has used chronic azithromycin, it must be discontinued for at least 4 weeks prior to randomization.

Zafirlukast will not be permitted.

Treatments with other Investigational Medicinal Products (IMPs) or previous therapies within four weeks or five times half-life of the drug, whichever is longer, is prohibited prior to study screening and during the study.

11 ASSESSMENT OF EFFICACY

11.1 Methods and Timing of Efficacy Assessments and Analyses

11.1.1 Spirometry

Each clinical trial site will use their own spirometry equipment. Sites will ensure that spirometry equipment is calibrated before first spirometry measurement at each study visit. Spirometry will be measured according to current American Thoracic Society (ATS)/European Respiratory Society (ERS) spirometry guidelines at each visit [Miller 2005a; Miller 2005b; Wanger 2005; Pellegrino 2005]. Three acceptable maneuvers will be obtained and the largest value for FVC and FEV₁ will be recorded, even if they come from different maneuvers. The FEV₁/FVC ratio will be calculated from the recorded best FEV₁ and FVC. FEV₁, FVC, absolute values will be recorded in the eCRFs.

Historical values documented in the patient file will be used for the calculation of decline $\geq 10\%$ predicted FEV₁ over 24 months as requested in the Inclusion criteria.

It is well known that spirometry relies on the cooperation between the patient and examiner and that the results obtained will depend on technical as well as personal factors. Therefore, all efforts will be undertaken to have a particular patient assessed by the same examiner. To reduce the variability of the results, the method should be standardized as much as possible.

Within-maneuver acceptability criteria:

Individual spirograms are acceptable if:

- They are free from artefacts:
 - Cough during the first second of exhalation
 - Glottis closure that influences the measurement
 - Early termination or cut-off
 - Effort that is not maximal throughout
 - Leak
 - Obstructed mouthpiece
- They have good starts:
 - Extrapolated volume $< 5\%$ of FVC or 0.15 L, whichever is greater
- They show satisfactory exhalation:
 - Duration of ≥ 6 seconds or a plateau in the volume-time curve or if the patient cannot or should not continue to exhale

Between-maneuver acceptability criteria:

After three acceptable spirograms have been obtained, apply the following test:

- The two largest values of FVC must be within 0.150 L of each other

- The two largest values of FEV₁ must be within 0.150 L of each other

If both of these criteria are met, the test session may be concluded.

If both of these criteria are not met, continue testing until:

- Both of the criteria are met with analysis of additional acceptable spirograms
or
- A total of eight tests have been performed (optional)
or
- The patient cannot or should not continue

The three best values out of the performed maneuvers will be recorded in the eCRF.

Timing of spirometry measures is provided in [Section 10.1.4](#). Timing of spirometry measures in relation to administration of IMP is provided in [Section 13.2](#).

11.1.2 SF-36 Quality of Life Questionnaire

The SF-36 Version 1.0 is a standardized, short form measure of generic health status, designed for self-administration. It takes 5-10 minutes for the patient to complete the questions. Patients will be asked to complete the questionnaire at Visits 1 (Baseline), 2, 3, 4, 5, and results will be entered into the eCRFs by the site staff.

12 ASSESSMENT OF SAFETY

12.1 Safety Parameters

Safety assessments at every visit include AE reporting, physical examination, CGI assessment, vital signs and clinical laboratory parameters (performed at the local labs in each study site).

L-CsA pharmacokinetic measurements at Visits 1 to 5 are analyzed at the Central Laboratory ACC GmbH in Germany, and also listed in this section, although they will not be available for immediate safety assessment by the DMC or Investigator.

COVID-19 specific consideration: In case the planned on-site visit cannot be performed due to COVID-19 restrictions, the PI or the Sub-Investigator and/or an appropriately qualified site study team member must call the patient. A remote visit must be performed to assess any potential adverse events (AEs) and to confirm the patient's status and well-being (see also [Section 13.2.7](#)).

12.1.1 Definitions

Adverse Event (AE)

An AE is any untoward medical occurrence in a patient after administration of a pharmaceutical product and which does not necessarily have a causal relationship with this treatment. An AE can therefore be any unfavorable and unintended sign (including an abnormal laboratory finding), symptom, or disease temporally associated with the use of a medicinal (investigational) product, whether or not related to the medicinal (investigational) product (ICH Guidelines for Good Clinical Practice E6(R2), 9 November 2016).

This includes worsening of a pre-existing condition or increase in frequency of a pre-existing condition. An AE is considered serious if it meets any of the serious criteria listed below. To ensure no confusion or misunderstanding of the difference between the terms “serious” and “severe”, which are not synonymous, the following clarification is provided:

The term “severe” is often used to describe the intensity (severity) of a specific event (as in mild, moderate, or severe myocardial infarction); the event itself, however, may be of relatively minor medical significance (such as severe headache). This is not the same as “serious”, which is based on patient/event outcome or action criteria usually associated with events that pose a threat to a patient’s life or functioning. Seriousness (not severity) serves a guide for defining regulatory reporting obligations.

The official definition also extends to AEs occurring during the off-treatment follow-up period.

Each patient will be closely observed and questioned for AEs throughout the clinical trial period with non-leading questions (e.g., how do you feel?). The patients will be instructed to report to the clinical trial staff immediately any symptoms and/or signs which occur between the scheduled observation times.

All AEs reported by the patient or observed by the Investigator or hospital personnel will be documented in the respective eCRF. The following information regarding each AE will be obtained: date and time of onset and resolution (duration), serious or non-serious (as defined below), severity, treatment required, outcome, relationship to certain medication, and if the AE caused withdrawal from the clinical trial.

In addition to the Investigator's own description of the AE, each AE event will be coded by data management according to the Medical Dictionary for Regulatory Activities (MedDRA) code list. The verbatim term will be recorded in the eCRF.

Abnormal laboratory test results will be reported as AEs if they are indicative of a clinical condition that meets the criteria for an AE.

Adverse Drug Reaction (ADR)

Adverse drug reactions (ADRs) are all noxious and unintended responses to a medicinal product related to any dose that a causal relationship between the medicinal product and an AE is at least a reasonable possibility, i.e., the relationship cannot be ruled out. An unexpected ADR is any adverse reaction not identified in nature, frequency, or intensity listed in the referent safety section of the current IB.

Serious Adverse Event (SAE)

Each AE is to be classified by the Investigator as SERIOUS or NON-SERIOUS.

The International Conference on Harmonisation (ICH) of Technical Requirements for Registration of Pharmaceuticals for Human Use defines an SAE as any AE occurring at any dose that results in any of the following outcomes:

- Death
- A life-threatening event (immediate risk of death at the time of the event)
- Inpatient hospitalization or prolongation of existing hospitalization
- A persistent or significant disability/incapacity
- A congenital anomaly/birth defect
- Other important medical event (Medical and scientific judgment should be exercised in deciding whether expedited reporting is appropriate in other situations, such as important medical events that may not be immediately life-threatening or result in death or hospitalization but may jeopardize the patient or may require intervention to prevent one of the other outcomes listed in the definition above. These should also usually be considered serious.)

12.1.2 Relationship to Clinical Trial Treatment Assignment

All AEs will be evaluated by the Investigator for potential relationship to the clinical trial treatment assignment (L-CsA or placebo) in the following categories:

- **Unrelated:** An AE with a known cause other than the use of IMP (no reasonable relationship).
- **Possible:** An AE that might be due to the use of the IMP. An alternative explanation, e.g., concomitant drug(s), concomitant disease(s), is inconclusive. The relationship in time is reasonable; therefore the causal relationship cannot be excluded (reasonable relationship).
- **Definite:** An AE that follows a reasonable temporal sequence from administration of the IMP; that follows a known or expected response pattern to the suspected clinical trial treatment assignment (reasonable relationship).

In the absence of information on causality provided by the reporting investigator, the sponsor will consult the investigator and encourage him/her to give an opinion on this event. The causality assessment given by the investigator will not be downgraded by the sponsor. If the sponsor disagrees with the investigator's causality assessment, the opinion of both the investigator and the sponsor will be provided.

12.1.3 Maximum Intensity

All AEs will be graded according to the following:

- **Mild:** Event requiring no special treatment and generally does not interfere with usual activities.
- **Moderate:** Event that impairs usual activities but may be ameliorated by simple therapeutic maneuvers.
- **Severe*:** Event which impairs usual activities and requires intervention.

* There is a distinction between a severe AE and an SAE; a severe reaction is not an SAE unless it meets one of the criteria for serious events (see [Section 12.1.1](#)).

12.1.4 Serious Adverse Event (SAE) Reporting

Any SAE occurring

- between the first clinical trial procedure after obtaining informed consent and within 2 weeks after the completion of the EoT Visit, whether or not considered related to the clinical trial treatment assignment.
or
- at any time after completion of the last follow-up and coming to the attention of the Investigator, if it is judged as related to the patient's participation in the clinical trial

must be reported to the Sponsor's Drug Safety (CCl) IMMEDIATELY, but within 24 hours upon knowledge, as follows:

- Document the event in the eCRF within 24 hours of discovery
- Submit the SAE report by Fax or e-mail to a list of predefined recipients
- Follow-up the SAE until the outcome is determined, providing periodic updates in the eCRF
- Provide any additional information if requested

Contacts of the Sponsor's Drug Safety are as follows:

CCI [REDACTED] [REDACTED] [REDACTED] [REDACTED] Belgium	Fax: CCI [REDACTED] Phone: CCI [REDACTED] E-Mail: CCI [REDACTED]
--	---

12.1.4.1 Timelines for Suspected Unexpected Serious Adverse Reaction (SUSAR) reporting to Competent Authorities and ECs

All suspected unexpected serious adverse reactions (SUSARs) will be reported by the Sponsor to the Competent Authorities and to the ECs concerned as soon as possible, but within a maximum of 15 days (fatal or life-threatening SUSARs within a maximum of 7 days) of first knowledge.

Relevant follow-up information of fatal or life-threatening SUSARs will be communicated subsequently within an additional 8 days.

12.1.4.2 Other Events to be treated as Serious Adverse Events

Exposure to drug during pregnancy/lactation:

In principle, pregnancy and the lactation period are exclusion criteria. In the event of a pregnancy occurring during the course of the clinical trial, the patient must be withdrawn from all IMP treatment immediately and permanently. The Sponsor must be notified without delay by completing the Pregnancy Form A and the patient followed during the entire course of the pregnancy and postpartum period. Prenatal and neonatal outcomes must be recorded even if they are completely normal and without AEs. The pregnancy reporting timelines are the same as described for SAE reporting procedure in [section 12.1.4](#).

If any clinical trial patient becomes pregnant during the clinical trial period, the Investigator must contact Zambon SpA as the Sponsor of the clinical trial or its designee to discuss the management of the patient.

Adverse Device Effect

In principle, serious adverse events caused by a device issue should be reported as SAEs as described above.

Other device deficiencies and malfunctions not associated with the adverse event should be reported via the **CCI** Complaint Form, provided in the IMP manual.

COVID-19 specific considerations:

All confirmed cases of COVID-19, occurring after the patient has provided informed consent and until 4 weeks after the EoT visit, must be reported as SAE and reported to **CCI** within 24 hours upon knowledge.

The seriousness criterion for COVID-19 hospitalized patients should be “hospitalization”; if the patient was not admitted to a hospital or the event is not resulting in prolonged hospitalization, the seriousness criterion “medically significant” should be used.

In all cases, details of the patient's symptoms, treatment and any clinically relevant information, should be entered in the SAE forms, as appropriate.

12.1.4.3 Investigational Medicinal Product (IMP) Overdosing

An overdose is a deliberate or inadvertent administration of a treatment at a dose higher than specified in the protocol. For the purposes of this clinical trial, any dose of aerosolized IMP administered to a patient that exceeds the dose foreseen in the protocol by more than 50% over 4 weeks should be reported as an overdose. Any occurrence of overdose are to be reported through the SAE procedures described above.

12.1.4.4 Events not regarded as Adverse Events/Serious Adverse Events

The following events will be not regarded as AEs/SAEs:

- Not applicable

12.1.4.5 Duration of Follow-up after Adverse Events

All AEs should be followed until they are resolved or until a stable clinical endpoint is reached. The occurrence of AEs and SAEs will be monitored until 2 weeks after the EoT visit.

12.1.5 Tolerability of IMP

Local tolerability findings will be recorded as AEs in the appropriate eCRF.

The patient will be observed for local tolerability findings for 1 hour after inhalation at each on-site study visit.

Local tolerability events are:

- Cough
- Wheezing
- Bronchospasm

- Throat irritation
- Change in FEV₁

In addition, these events will be solicited actively before IMP inhalation at each study visit (except EoS) by questioning the patient whether he/she has experienced any of the events in-between the study visits. If applicable, an AE report form will be completed.

Overall tolerability assessment by the investigator includes:

- CGI questionnaire ([Guy 1976](#))
- Investigator's tolerability assessments at Visit 3 and Visit 5, assessed by means of a five-point verbal rating scale with the response options 'very good', 'good', 'satisfactory', 'moderate', and 'poor'

12.1.6 Clinical Laboratory

Laboratory assessments will be performed following the routine protocols at each on-site visit by the local laboratory at each site.

The following clinical laboratory parameters have to be documented:

- White blood cell count with differential
- Red blood cell count
- Platelet count
- Alkaline phosphatase
- Alanine aminotransferase
- Aspartate aminotransferase
- Gamma glutamyl transferase
- Blood urea nitrogen
- Serum bilirubin
- Serum creatinine

Laboratory assessments listed above will be performed at a local facility, checked and interpreted by the investigator and entered into the appropriate section of the eCRF. The Normal Laboratory Ranges of each local laboratory will be used for the the assessment of clinical significance.

12.1.6.1 Pregnancy Test

Serum or urine samples from women of childbearing potential will be collected for pregnancy tests at Screening, and on-site Visits 1, 2, 3, 4, 5, and 6. Positive results will be recorded in the eCRF and appropriate actions will be taken.

12.1.6.2 Pharmacokinetic Parameters

Whole blood samples for determination of cyclosporine A will be collected at Visit 1 pre-dose, directly after end of inhalation; and 15, 30, and 45 minutes (+/- 5 minutes), and 1, 1.5, 2, and 4

hours (+/- 15 minutes) after end of inhalation for determination of C_{max} , t_{max} , and AUC_{0-4h} . PK analysis will be performed in a central laboratory (CCI [REDACTED]).

All sites will be provided with specific Laboratory Kits for collecting the PK blood samples. Blood should be collected into the respective pre-labelled K2-EDTA Tubes and should be stored at -20°C immediately after collection until shipment to the central laboratory.

Instruction on handling, processing, storage and shipment are in detailed described in the Laboratory Manual for Pharmacokinetic Blood Sampling.

12.1.6.3 Cyclosporine A Whole Blood Trough Levels

A whole blood sample for the determination of cyclosporine A trough level will be collected at Visit 2 to Visit 5 at each on-site visit. The sample should be collected 15 minutes before inhalation. The trough levels of CsA at visit 2 to 5 will be analysis will be performed in a central laboratory (CCI [REDACTED]).

All sites will be provided with specific Laboratory Kits for collecting the PK blood samples. Blood should be collected into the respective pre-labelled K2-EDTA Tubes and should be stored at -20°C immediately after collection until shipment to the central laboratory.

Instruction on handling, processing, storage and shipment are in detailed described in the Laboratory Manual for Pharmacokinetic Blood Sampling.

12.1.7 Vital Signs

Vital signs will be assessed at each on-site visit.

The following vital signs will be recorded:

- Systolic and diastolic blood pressure (sitting, after minimum 5 minutes of rest),
- pulse rate (sitting, after minimum 5 minutes of rest),
- body temperature (the same method should be used for each patient and throughout the clinical trial),
- respiratory rate.

12.1.8 Physical Examinations

A physical examination will be carried out at the Screening Visit and at every subsequent on-site visit. The following body systems will be examined: body weight and height (at Screening visit only), cardiovascular, respiratory, nervous, gastrointestinal, hepatic, renal, dermatological, musculoskeletal, extremities, eyes, ears, nose, throat, and lymphatic.

Abnormal findings will be summarized for each patient and will be documented as AE.

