### **9.1.1 Imputation of Missing data**

There will be no imputation of data for efficacy analysis. All data will be analyzed as they appear in the database. Missing data will be displayed in subject data listings and will be declared in tables as appropriate.

The following imputation rules will apply only for AE data:

- Imputed data should be flagged and properly footnoted as “imputed”.
- AEs with unknown onset date/time will be counted as treatment emergent AEs (TEAEs).
- AEs/TEAEs with unknown end date/time will be counted as an ongoing AEs/TEAEs, unless ongoing was ticked on the CRF.
- TEAEs will be considered potentially IMP related if the investigator’s rating of the causal relationship is anything other than ‘not related’ or missing.
- If for the calculation of a time period the full date format ddmmmyyyy is needed, missing entries will be imputed as follows:
  - Missing day in start date of a time period is imputed by the first day of the month;
  - Missing day in stop date of a time period is imputed by the last day of the month;
  - Missing month in start date of a time period is imputed by January of the year;
  - Missing month in stop date of a time period is imputed by December of the year;
  - Missing year is not imputed.

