### **13.3.2 Laboratory measures, vital signs, physical examination**

For clinical safety laboratory test results and vital signs, the numeric values and corresponding changes from baseline will be summarized using descriptive statistics by parameter and time point for the following parameters:

Hematology (Basophils, Basophils/Leukocytes, Eosinophils, Eosinophils/Leukocytes, Lymphocytes, Lymphocytes/Leukocytes, Monocytes, Monocytes/Leukocytes, Neutrophils, Neutrophils/Leukocytes, Platelets, Erythrocytes, Leukocytes)

Chemistry (Alkaline Phosphatase, Alanine Aminotransferase, Aspartate Aminotransferase, Bilirubin, Creatinine, Gamma Glutamyl Transferase, Urea Nitrogen)

Vital Signs (Systolic and diastolic blood pressure, Heart Rate, Body Temperature, Respiratory Rate.)

In addition to the tables showing the distribution parameters, laboratory measures will be presented in ‘shift tables’ that show the position of all patients relative to the applicable reference range at clinical trial entry, broken down by the position at V3 and at EoT.

---

For physical examination results, tables of frequencies will be prepared, broken down by treatment group and visit.

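### Protocol 12.1.8 records abnormal physical findings as AEs with no new-or-worsened condition, so chronic findings of unknown or late-recorded onset can be counted as TEAEs

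*Protocol*

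**What the plan says.** Protocol 12.1.8 sets the timing: "A physical examination will be carried out at the Screening Visit and at every subsequent on-site visit". The systems examined include respiratory, dermatological, hepatic, musculoskeletal and eyes. The section ends: "Abnormal findings will be summarized for each patient and will be documented as AE". Nothing requires the finding to be new, worse or clinically relevant.

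Other parts of the protocol are narrower:

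- Protocol 12.1.1: "An AE is any untoward medical occurrence in a patient after administration of a pharmaceutical product". On existing disease it adds: "This includes worsening of a pre-existing condition or increase in frequency of a pre-existing condition". An unchanged condition is not named.
- Protocol 12.1.1, on laboratory values: "Abnormal laboratory test results will be reported as AEs if they are indicative of a clinical condition that meets the criteria for an AE". Physical findings have no such filter.
- Protocol 13.2.1 sends significant conditions arising before consent to medical history and names cGvHD in another organ among them.
- Protocol 12.1.4.4, the place for events not regarded as AEs, lists none.

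In the SAP, Sections 10.3.1 and 13.3.1 define a TEAE as an event starting on or after first IMP intake, or a pre-existing one that worsens afterwards. An onset dated before first dose makes it Non-TEAE. For missing onset, SAP 9.1.1 says: "AEs with unknown onset date/time will be counted as treatment emergent AEs (TEAEs". SAP 13 places an event with a missing or incomplete onset in the 4-week analysis if it could have begun by Visit 3. On the examination itself, SAP 13.3.2 says: "For physical examination results, tables of frequencies will be prepared, broken down by treatment group and visit".

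**The concern.** BOS and documented cGvHD are entry criteria (Protocol 9.1), and Protocol 6.1.8 describes the cGvHD as being in an organ other than the lung. Abnormal findings at entry are therefore foreseeable. A site that follows 12.1.8 literally enters them as AEs. A site that follows 12.1.1 and 13.2.1 does not. With up to 20 centers and 24 patients, the two readings may well coexist.

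At stake is the main safety comparison. TEAE proportions, their pairwise comparisons at SOC level and the incidence densities all stand under Primary Assessments in the SAP. With 8 patients per arm, one misclassified patient moves an arm's proportion by 1/8 = 12.5 points.

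**Working it through.** **Step 1: where a chronic finding ends up under the current text**

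| How the finding is recorded | Rule that applies | Result |
|---|---|---|
| Medical history only | Protocol 13.2.1 | Not an AE |
| AE, onset dated before first dose, not worsened | SAP 13.3.1 | Non-TEAE |
| AE, onset unknown, even if seen at Screening | SAP 9.1.1 and 13 | TEAE, can fall in the 4-week window |
| AE, first noted after dosing and dated to that visit | SAP 10.3.1 and 13.3.1 | TEAE |

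The last two rows are the leak. The after-administration clause in Protocol 12.1.1 does not close it, because AEs are also listed among the activities at Screening (13.2.1) and at Visit 1 before treatment (13.2.2). For the window, SAP 13 borrows the incomplete-date procedure of SAP 12, which takes the earliest possible date. This favors inclusion by Visit 3.

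**Step 2: which outputs are exposed**

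- Exposed: the any-TEAE row, the SOC and PT tables, the SOC-level pairwise comparisons and the incidence densities for all TEAEs (SAP 13.3.1).
- Protected: the local tolerability comparisons, since SAP 13.1 requires a named PT that newly appeared within 1 hour of an inhalation.
- Largely insulated from stable chronic findings: the tables of serious, severe and treatment-related TEAEs and of TEAEs leading to discontinuation.

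**Step 3: the plan's own figure**

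The plan gives 3 × 8 = 24 patients, set by feasibility. It states no power, effect size or event rate, so there is no further figure to reproduce.

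**Step 4: illustration with assumed inputs**

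Let p be the true proportion with a TEAE in one SOC. Let b be the share of otherwise event-free patients who receive a chronic finding counted as a TEAE in that SOC. Then

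p′ = p + b(1 − p),

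and if b is equal in both arms, difference′ = (1 − b) × difference.

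Assume 12.5% on placebo and 62.5% on L-CsA. The last two columns give the chance that a 95% interval for the difference lies wholly above zero, by exact binomial enumeration. The interval is Newcombe's, built from Wilson limits. The SAP names only Wilson score intervals, so this choice is an assumption.

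| b | Placebo | L-CsA | Difference (points) | 8 v 8 | 16 v 8 (pooled) |
|---|---|---|---|---|---|
| 0 | 12.5% | 62.5% | 50.0 | 63% | 72% |
| 0.10 | 21.3% | 66.2% | 45.0 | 54% | 61% |
| 0.25 | 34.4% | 71.9% | 37.5 | 41% | 47% |
| 0.50 | 56.2% | 81.2% | 25.0 | 20% | 29% |
| 0.75 | 78.1% | 90.6% | 12.5 | 4% | 10% |

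With 25% v 75% the differences are the same and the chances similar (63% and 71% at b = 0; 18% and 30% at b = 0.50).

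In counts, 5/8 v 1/8 is a difference of 50 points with interval 3 to 76. If one more L-CsA patient and three more placebo patients acquire a chronic-finding TEAE, it becomes 6/8 v 4/8: 25 points, interval −19 to 59.

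**Step 5: unequal misclassification**

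Take b = 0.25 in one arm only:

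- L-CsA only: 0.625 + 0.25 × 0.375 = 0.719. The difference is 0.719 − 0.125 = 59.4 points, which exaggerates the true 50.
- Placebo only: 0.125 + 0.25 × 0.875 = 0.344. The difference is 0.625 − 0.344 = 28.1 points, which understates it.

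**The case against.** The strongest reply is that 12.1.8 should not be read alone. Protocol 12.1.1 speaks of occurrences after administration and of worsening. Protocol 13.2.1 already sends known cGvHD to medical history, and 12.1.1 asks for an onset date and time for every AE. Dated pre-dose events drop out of the TEAE tables, and counting unknown onset as treatment-emergent is a conventional conservative choice. The eCRF Completion Guidelines (Protocol 20.2) are not among the documents and may settle the matter. The analysis is declared descriptive, and with 8 per arm the intervals are wide anyway.

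Much of this stands, and it rules out several stronger readings that a reader might infer:

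- *Every abnormal finding becomes an AE.* The text conflicts with itself, so this is a risk and not a certainty.
- *Chronic findings generally become TEAEs.* Only unknown or late-dated onset leads there. The documents do not say how often onset would be unknown.
- *Arm differences are diluted.* That needs similar misclassification across arms. Protocol 8.3.1 blinds only the patients, so the direction is open.
- *New findings cannot be identified at all.* SAP 9.1 promises change from baseline for repeated outcomes, and listings of all eCRF data. The lack of an examination shift table is therefore secondary.

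The reply does not remove the conflict. Neither 12.1.1 nor 13.2.1 says how to record a sign seen at the Screening examination after consent, or a chronic sign first written down later. There, 12.1.8 is the specific instruction. A conservative rule for unknown onset is also hard to defend for a finding that was documented before the first dose.

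**Conclusion.** The point holds as a conflict of wording with a limited but real path into the primary safety summaries. Followed literally, the rules can classify a finding seen before dosing as a TEAE when its onset is left unknown. They do the same with a chronic finding that is first noted and dated after dosing.

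The size and direction of the effect cannot be found from the documents. The event rates and every value of b above are assumptions that show only how the mechanism works. For a SOC comparison, b counts only findings in that SOC, so it will not exceed the share for any-TEAE. The correction is worth making because it is cheap and the affected tables are primary, not because harm to the results has been shown.

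**What to change.** **Protocol 12.1.8.** State that:

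- findings present at Screening go to medical history;
- findings arising between Screening and first dose are recorded with a pre-dose onset date, and so are Non-TEAE;
- after dosing, only findings that are new or worsened since the last pre-dose examination, and that meet the 12.1.1 definition, are documented as AEs, with onset at the date first seen or worsened.

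Keep the worsening wording of 12.1.1. A stricter threshold, such as clinically significant worsening, would exclude events that 12.1.1 treats as AEs and create a new conflict.

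**SAP 9.1.1.** Add that an AE with unknown onset that matches a finding recorded at Screening or at Visit 1 before dosing is not counted as a TEAE unless it worsened. Changing 12.1.8 alone would leave this rule in force for AEs already entered.

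**SAP 13.3.2 (optional).** Show physical examination by body system as a shift from Visit 1 to Visit 3 and to EoT.

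**Cost.** A few sentences, a matching line in the eCRF Completion Guidelines, one table format if the shift table is adopted, and a review before database lock of examination AEs already entered. That review is best done without treatment assignment, in the format that SAP 10.2 sets for the blind data review meeting.
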